The PI or research staff give the participant study medication (losartan or placebo). The PI or research staff goes over the instructions for taking the study medication which includes how many pills to take and at what times of day, potential side effects, and who to call if they have questions or problems while taking the medication.

Visits 3 and 6 - Pick up 24 hour blood pressure monitor (approximately 15 minutes)

The PI or research staff instrument the participant with the 24 hour blood pressure monitor. The PI or research staff goes over the instructions for wearing the monitor.

Visits 4 and 7 - Experimental visits (approximately 4 hours each)

Note: prior to coming to PSRB for the experimental visits, subjects take the oral study medication for 6 weeks. Subjects will ingest 1 pill per day. After the first study visit, subjects will undergo a washout period of at least 14 days in which they do not ingest any study medication, before beginning the same 6 week regimen of the other treatment.

In the event of an experimental failure (e.g. equipment stops working, building power outage during study visit, etc) subjects may be asked to repeat a trial.

Experimental procedures

24 hours before the study visit, subject will be instrumented with a 24 hour blood pressure monitor to wear home for 24 hours. Subject will return the blood pressure monitor to the investigators when they come in for the experimental visit.

Subjects will come to the CRU or 118 PSRB where a research nurse or approved laboratory personnel performs a blood draw (14.5 ml, < 1 Tablespoon) for substances of interest (e.g. inflammatory cytokines) and immune cell activity, and blood chemistry. The subject provides a urine sample for the measurement of urine proteins which will be measured by the UI Diagnostic Lab. Then the rest of the study visit occurs in 118 PSRB for the experiment (Pulse wave velocity and intradermal microdialysis).

Pulse wave velocities (PWV) on Carotid-femoral and carotid-brachial: Carotid-femoral artery PWV, the 'gold standard' in vivo assessment of aortic

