Experimental visits: \$100 per visit (\$15/microdialysis probe + \$10 for pulse wave velocity measurements + \$7.50/hour for completing the experiment)

Total for completing the study: \$280 (two pre-treatment periods, two 24 hour blood pressure monitors, two completed study visits)
 Parking pass for time involved at study and screening visits.

Pro-rating: Subjects can receive payment for pre-treatment and experiments not completed. The researchers pay an amount of money equal to the part completed. For instance, if a subject completes half of Experiment 1, the subject receives \$15.00 for each probe inserted plus \$7.50 for each hour they completed. The researchers may ask subjects to repeat a trial. If subjects agree to repeat a trial, they receive payment for the repeated trial as stated above.

VIII. Risks

VIII.1

What are the risks to subjects including

- emotional or psychological*
- financial*
- legal or social*
- physical?*

Physical Risks:

Microdialysis: Intradermal microdialysis is a specialized research technique. [name] is highly skilled in this technique and has been using the procedures in this protocol (including fiber placement, perfuse preparation, subject monitoring, and fiber removal) for over 10 years with no adverse events and have been reviewed and approved by [name] at the University of Iowa.

Cutaneous microdialysis commonly causes some pain and bruising similar to that experienced during venipuncture. There is usually no pain after the probe is in place. The participant may experience mild pain while the researchers remove probe. Minor bleeding may occur. As with any event that breaks the skin, infection is possible. However, no participants in any of the researchers' prior experiments have reported infection. In the unlikely event in which the membrane breaks during removal leaving an isolated piece of membrane under the skin, they treat the piece of membrane in a manner similar to that for a splinter in the skin. In this case, trained personnel make a superficial incision for removal. Such an event has never occurred in any projects overseen by [name].

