The -80C freezer in 111 PSRB is a shared wet lab space. The door to this lab space is kept locked but those with keys to the shared lab space would be able to enter the room. Individuals with key access to 111 PSRB include:

[name]
[name], BS
[name], BA

X.7***Does your study meet the NIH criteria for a [Certificate of Confidentiality](#) or will you be applying for Certificate of Confidentiality?***

Yes

X.8***If yes, provide rationale:***

Per Section 2012 of the 21st Century Cures Act as implemented in the 2017 NIH Certificates of Confidentiality Policy, all ongoing or new research funded by NIH as of December 13, 2016 that is collecting or using identifiable, sensitive information is automatically issued a CoC.

XI. Data Analysis**XI.1*****Describe the analysis methods you will use, including, if applicable, the variables you will analyze***

The primary outcome variable will be cutaneous vascular conductance, which is calculated from laser-Doppler flux/mean arterial pressure. Three-way repeated measures ANOVA (treatment, MD site, dose) will be used to examine systemic treatment differences (losartan vs. placebo) and local

microdialysis treatment differences across the doses of pharmacological stimuli. Appropriate post-hoc analyses with corrections for multiple comparisons will be performed when main effects are identified, including potential confounding variables as covariates. Paired t-tests will be used to examine systemic treatment differences on pulse wave velocity.

XI.2***Provide the rationale or power analysis to support the number of subjects proposed to complete this study.***

Based on previous data examining chronic pharmacological intervention strategies we calculate that 10 subjects will be necessary to detect an effect size of 15% between microdialysis sites (1 sample RMANOVA, power=0.08, $\alpha=0.05$). Based on the duration of the intervention and prior experience, we anticipate that ~5 subjects will screen but not be eligible and of those that enroll, ~5 will drop out of the intervention, therefore, we suggest a total sample of 20 subjects.

XII. Future Research**XII.1*****Do you wish to keep any information about subjects involved with this research project so that members of the current research team may contact them in the future for your own research projects?***

Yes

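### A lost acetylcholine probe or dose reading can remove a woman from the planned repeated measures ANOVA, and the sample size leaves no spare completers

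*Combined protocol and SAP*

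**What the plan says.** Section XI.1 states: "The primary outcome variable will be cutaneous vascular conductance". It analyses this by a "Three-way repeated measures ANOVA (treatment, MD site, dose"). It names no missing-data rule, analysis population or mixed model.

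Section XI.2 says that "10 subjects will be necessary to detect an effect size of 15% between microdialysis sites". It reaches a total of 20 by adding about 5 women who fail screening and about 5 who drop out.

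Section VII.E.6 describes four probes per visit. Probes 1 and 2 carry 10 acetylcholine doses, without and with L-NAME. Probe 3 carries 9 doses of angiotensin II and probe 4 carries 9 doses of norepinephrine. The same section foresees lost experiments: "In the event of an experimental failure (e.g. equipment stops working, building power outage during study visit, etc"), after which a repeat may be requested. Section VII.E.19 makes the repeat voluntary: "If subjects agree to repeat a trial, they receive payment for the repeated trial as stated above". It also pays pro rata for an experiment that is only half finished.

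**The concern.** A conventional repeated measures ANOVA works on a complete within-woman record. Only the acetylcholine probes provide two sites on a common dose series, so treatment x site x dose describes that analysis alone. One unusable acetylcholine probe, or one unusable dose, at either visit then costs all of that woman's acetylcholine data, including a full series from her other visit.

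The protocol expects some experiments to fail or stop early, and repeats depend on the woman's agreement. The enrolment sum allows for screen failures and dropouts, but not for partial data among women who finish both periods. Power could therefore fall although every planned completer attends, and usable data from two four-hour invasive visits would be discarded.

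**Working it through.** **Inputs.** 10 women, an effect of 15%, alpha 0.05 and power printed as 0.08 (XI.2); 2 acetylcholine sites and 10 doses (VII.E.6); two-period crossover (VII.D.29). Assumptions: the printed power means 0.80, the test is two-sided, and loss rates are net of repeats. The documents give no standard deviation, within-woman correlation or failure rate.

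**1. The plan's own figures.** The accrual sum reproduces: 20 - 5 - 5 = 10. The 10 itself cannot be reproduced without a standard deviation, so I solved backwards. For a two-level within-woman contrast the ANOVA F test equals a paired t-test, with power(n) = P[T(n-1, d√n) > t(0.975, n-1)], where T is noncentral t. Power 0.80 at n = 10 gives d = 0.996. If the effect is 15 units, the SD of within-woman differences is 15/0.996 = 15.1. Taken literally, power 0.08 would imply an SD of about 84, so it looks like a misprint.

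**2. Cost of each lost woman,** with d = 0.996: 10 women, 80.0%; 9, 74.5%; 8, 67.7%; 7, 59.7%; 6, 50.4%.

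**3. Probe losses.** A complete record needs 2 sites x 2 visits = 4 probe-sessions. If each is lost independently with probability q, a woman is complete with probability p = (1-q)^4. The number complete is Binomial(10, p), and power is averaged over it.

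| q (assumed) | p | Expected complete of 10 | Chance of losing at least one, 1 - p^10 | Average complete-case power |
|---|---|---|---|---|
| 1% | 0.961 | 9.6 | 33% | 78% |
| 2% | 0.922 | 9.2 | 55% | 75% |
| 5% | 0.815 | 8.1 | 87% | 68% |
| 10% | 0.656 | 6.6 | 98.5% | 54-55% |

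**4. Single-dose losses.** If 0.5% of readings were lost independently, 0.995^40 = 0.818, so about 8.2 of 10 women would be complete.

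**5. Mixed model for comparison.** Simulations of 1,500 runs per setting, under two assumed variance structures, tested the treatment main effect by generalised least squares on all observed readings:

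- 2% of probe-sessions lost: 78-79%, against 73-75% for complete cases.
- 5% lost: 79-80%, against 69%.
- 10% lost: 76-77%, against 54-55%.
- 0.5% of single readings lost: 79-80%, against 69-70%.

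Monte Carlo error is about one point (√(0.79 x 0.21/1500) = 0.0105), so the small rise between 2% and 5% is noise. For site and treatment x site, each set to 80% at n = 10 and with assumed variances of 1.0 (woman), 0.35 (visit) and 0.35 (probe), the mixed model gives about 79%, 76% and 72% at 2%, 5% and 10% loss. All these figures treat the variances as known, so they are best cases.

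**6. Choice of random effects.** With the same variances, complete data and no true effect, a model with random effects for woman and visit only rejects far too often. At dose residual variances of 0.1, 0.35 and 1.0, its false-positive rates for site and treatment x site are about 60%, 46-48% and 31%, at a nominal 5%. The repeated measures tests of the same contrasts stay near 5%. Without a probe term, ten doses from one probe count as nearly independent replicates, and Kenward-Roger cannot repair an omitted variance component.

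**The case against.** The strongest reply is that the loss may be small. No failure rate is given, and repeats are provided for and paid. At 1% net loss there is a 67% chance that no woman is lost, and average power is still 78%. At 2% the gap is about 75% against 79%. This stands: the size is conditional. Repeats lower the rate but guarantee nothing.

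A second reply is that listwise deletion is not written down. That is true. It follows from the named method, and section X.4 mentions SPSS datasheets without naming a procedure. If the team intends a mixed-model fit, the plan should say so.

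A third is that flow is recorded continuously and a power outage would take out a run of doses together. Clustered losses remove fewer women than the independent-loss figure in step 4, which is therefore pessimistic for a given number of lost readings.

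Stronger readings that a reader might infer are not supported:

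- *Any failed probe removes the woman altogether.* A lost angiotensin II or norepinephrine probe affects only that drug's analysis, and the paired t-test of pulse wave velocity is untouched.
- *The analysis set will fall below 10.* It can; nothing in the documents shows that it will.
- *A mixed model would rescue the dropouts.* The treatment contrast is within woman, so a woman who misses a whole period adds little. The roughly 5 dropouts are already budgeted.
- *Any mixed model would do.* Step 6 shows that a poorly chosen one is worse than the planned ANOVA for the L-NAME site contrast on which Hypothesis 1 (I.5) rests.

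**Conclusion.** The point holds for the acetylcholine analysis. The named method conventionally requires a complete 40-reading record, the head count has no margin above 10, and the protocol itself foresees partial experiments with only optional repeats. The first woman lost costs about 5.5 points of power (80.0% to 74.5%) and the second about 7 (to 67.7%). Over assumed net probe-session losses of 1% to 10%, complete-case power runs from about 78% down to 54-55%. A correctly specified mixed model would hold roughly 76-79% for treatment at 2-10% loss, with a smaller gain for site and treatment x site.

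This rests on power read as 0.80, a two-sided test, independent losses and assumed variances. The direction is secure; the size depends on a failure rate that only the sponsor can supply. It is a worthwhile, inexpensive correction and not a fatal flaw.

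**What to change.** In XI.1, replace the ANOVA for acetylcholine with a linear mixed model on all available readings:

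- Fixed effects: treatment, site, dose, their interactions, and period.
- Random effects: woman, woman-by-treatment (visit), woman-by-site, and probe within visit (woman-by-treatment-by-site). The last two make site and treatment x site be tested against the right error term.
- Kenward-Roger degrees of freedom.

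Fit the angiotensin II and norepinephrine series with the analogous treatment x dose model. State how lost doses, lost probes and repeated trials are handled. In XI.2, correct the printed power and give the SD behind the 10. Settle this before unblinding.

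The cost is wording and a standard software procedure, with no extra women, visits or probes. Keeping the ANOVA and adding completers instead would take 10/p: 11, 11, 13 or 16 completers at 1%, 2%, 5% or 10% loss. That is hard to reach with the last visit dated 08/31/2024 in VII.B.1.c and the document approved on 7/19/2024.

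The downsides are that missing values are assumed missing at random and that several variance components must be estimated from about 10 women. With complete data the tests of treatment, site and their interaction address the same questions as the ANOVA, apart from the added period term. Dose terms would be tested against the residual, so correlation between successive doses on a probe should be checked.

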- *Use 3rd person active voice "The Principal Investigator will identify subjects. For example, the principal investigator will identify potential subjects, the study coordinator will discuss the study with subjects over the telephone and schedule the first study visit, etc..."*
- *Describe the steps that will be taken by the research team to minimize the possibility of coercion or undue influence during the consent process*

The subjects will consist of healthy women (age 18 and older) who have delivered a baby within the past 5 years and had preeclampsia during their pregnancy, but were free of cardiovascular or metabolic disease prior to pregnancy. These subjects will be enrolled and complete losartan and placebo treatments in a double-blind randomized crossover design. The PI and research staff will recruit subjects from Johnson county and surrounding areas via advertisements, flyers, emails, The UI mass-email system, newspaper and newswire ads, Research Match.org, obtaining contact information from the Maternal Fetal Tissue Bank (MFTB) registry, utilizing TriNetX (discussed in more depth below), and posting on the UIHC website for research volunteers. Recruitment materials (attached MFTB recruitment letter) will be sent to women registered with the MFTB who fit our inclusion criteria and have consented to be contacted for future studies. The UIHC Clinical Trials and Research Website will have this research study available as a listed research study for potential research subjects to find out more information and express interest in participating. Additionally, paid advertisements (see attached IC Mom Ad) will be posted on the Iowa City Moms website and social medias. These advertisements when clicked will link to the study's page on the UIHC Clinical Trials and Research website.

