VII.E.2 *Describe randomization scheme/assignment including ratio such as 1:1, 2:1 etc.*
Subjects will be randomized to which treatment they receive first (placebo or losartan). All subjects will complete both arms of the study. They will be blinded to which treatment they are receiving at the time of the treatments. If they wish to know, subjects can be informed which treatment they received at what time when they complete the study.

VII.E.3 *Will any questionnaires, surveys, or written assessments be used to obtain data directly from subjects in this study?*
Yes

VII.E.4 *List all questionnaires, surveys, written assessments and ATTACH each one to the application. (NOTE: You are NOT prohibited from attaching copyrighted materials to this application)*
pre-consent screening survey
additional information survey
health history questionnaire

VII.E.5 *Does this project involve creating any audiotapes, videotapes, or photographs?*
No

VII.E.6 *Provide a detailed description in sequential order of the study procedures following the consent process - DO NOT cut and paste from the Consent Document.*

Describe study populations separately if they will be participating in different procedures - include CONTROL population if applicable.

DESCRIBE:

- *What subjects will be asked to do/what happens in the study (in sequential order)*
- *The time period over which procedures will occur*
- *The time commitment for the subject for individual visits/procedures*
- *Long-term followup and how it occurs*

Visit 1 - Consent and Screening (approximately 1 hour)

The PI or research staff explain the study and go over the informed consent with the participant. After the participant signs the informed consent, the PI or research staff performs the physical screening that includes urine pregnancy test, heart rate (HR), blood pressure (BP), height, waist circumference, and weight measurements. The participant fills out the health history questionnaire and confirms that they are using an effective form of birth control. A research nurse performs or approved laboratory personnel standard venipuncture to obtain blood (total = 7.5ml blood) for complete blood count (CBC), chemistry analysis, and lipid profile to be measured at UIHC pathology labs. The subject provides a urine sample for the measurement of urine proteins which will be measured by the UI Diagnostic Lab.

Visits 2 and 5- Pick up study medications (approximately 15 minutes)

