- Electronic records (computer files, electronic databases, etc.) - Electronic records (computer files, electronic databases, etc.) - Data will be entered using subject ID code into the ICTS REDCap web-based database application that is password protected. No personal identifiable data will be entered. Only research staff on the IRB approved study will be allowed access this database. The ICTS REDCap staff are responsible for maintaining security of the data. Some data using subject ID code will also be entered into a Microsoft Excel and SPSS datasheets that will be kept in a shared server for CLAS that is password protected. Only research staff on the IRB approved study will have access to the folder the study on the server.
 - Name - [name]
 - Title - IT Support Consultant
 - University Job Classification - Faculty/Staff

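### The unnamed covariates in XI.1 have no bias to remove from a within-woman crossover comparison and may do harm, while period, which can disturb that comparison, is left out

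*Combined protocol and SAP*

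**What the plan says.** Section VII.D.29 says that the women will "complete losartan and placebo treatments in a double-blind randomized crossover design". Section VII.E.2 adds: "Subjects will be randomized to which treatment they receive first (placebo or losartan). All subjects will complete both arms of the study". It gives no ratio, blocking or stratification.

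Section XI.1 defines the outcome: "The primary outcome variable will be cutaneous vascular conductance, which is calculated from laser-Doppler flux/mean arterial pressure". It then names the model: "Three-way repeated measures ANOVA (treatment, MD site, dose) will be used to examine systemic treatment differences (losartan vs. placebo) and local" microdialysis differences. The factors are treatment, site and dose; neither period nor treatment order is listed. The sentence after it is: "Appropriate post-hoc analyses with corrections for multiple comparisons will be performed when main effects are identified, including potential confounding variables as covariates".

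The covariates are not named. Nothing says whether they are baseline traits or values taken at each visit, whether they are centred, whether they interact with treatment, or whether they enter the main ANOVA as well as the post-hoc tests. Section VII.B.11 says there is no separate written protocol. The only software mentioned is in X.4, where some data go into "Microsoft Excel and SPSS datasheets"; that describes data storage, not model options.

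**The concern.** Adjusting for confounders makes sense when different people receive different treatments. Here treatment, microdialysis site and dose all vary within the same woman, and VI.13 describes a single population with no control group. The only between-woman factor is the randomised order. A fixed trait is the same under losartan and placebo, so there is nothing for the adjustment to correct.

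Three things are at stake. First, a repeated measures ANOVA that carries treatment-by-covariate terms tests a different hypothesis if the covariate is not centred. Second, a variable that losartan itself changes is not a confounder, and adjusting for it changes the question. Third, with about 10 completers, an open covariate list lets the reported result depend on which variables were tried. Meanwhile period, the one design factor that can bias or blur a two-period comparison, has no term.

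**Working it through.** **Inputs.** From XI.2: 10 completers, a 15% effect, alpha 0.05 and power printed as 0.08. Assumed: two-sided testing, 0.08 read as 0.80, and the covariate means and SDs in the table below.

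**The plan's own figure.** The count 20 − 5 − 5 = 10 reproduces. The sample size of 10 does not, because no SD or correlation is given. A paired t-test with n = 10 and 80% power needs a standardised difference of 0.996. For a 15-point effect that implies an SD of the differences of 15/0.996 = 15.1; at a power of 0.08 it would be about 84. XI.2 sizes the study on a difference between microdialysis sites, so 80% for losartan versus placebo is a benchmark, not the plan's claim.

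**Step 1: fixed trait as a main effect.** Write each woman's response as her own level + treatment effect + βx + error. In the losartan-minus-placebo difference, βx cancels. In one worked data set with a random intercept per woman, the estimate was 17.95 (SE 3.13) with age and without it.

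**Step 2: fixed trait with a treatment-by-covariate term, centred.** The difference is regressed on an intercept and k covariates, leaving 9 − k degrees of freedom. With noncentrality 0.996 × √10 = 3.15, power is 0.80 for k = 0 and 0.79, 0.77, 0.75 and 0.71 for k = 1 to 4.

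**Step 3: the same, uncentred.** The intercept is now the treatment effect at x = 0. Its variance is σ²(1/n + x̄²/Sxx), so the SE grows by about √(1 + (10/9)(mean/SD)²), and 3.15 is divided by that factor. The last two columns come from 20,000 simulated trials per setting.

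| Covariate (assumed mean, SD) | Mean/SD | SE factor | Noncentrality | Power, uncentred | Power, centred |
|---|---|---|---|---|---|
| Age (32, 5) | 6.40 | 6.82 | 0.46 | 0.07 | 0.79 |
| Entry BMI (28, 6) | 4.67 | 5.02 | 0.63 | 0.09 | 0.79 |
| Months since delivery at entry (30, 17) | 1.76 | 2.11 | 1.49 | 0.26 | 0.79 |

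In the worked data set, raw age gave 5.9 (SE 19.1, p = 0.77); centred age gave 17.95 (SE 3.24, p = 0.0006). If all 15 enrolled women finished (20 − 5), power would be 0.95 without covariates, 0.09 with raw age and 0.95 with centred age.

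**Step 4: on-treatment variables.** VII.E.6 has blood pressure recorded over 24 hours before each experimental visit and again during it. VIII.1 says the drug may lower it. Mean arterial pressure is also the denominator of the primary outcome. In an illustrative simulation, adjusting for a variable that losartan changes moved the estimate from 14.9 to 10.1. The size depends on the assumed strength of the pathway; the direction is the point.

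**Step 5: period.** Assume a 7:3 split of treatment orders and a period effect that shifts the within-woman difference by 5 points, up in one order and down in the other. The unadjusted mean is 15 + 5 × (7 − 3)/10 = 17.0 against a true 15; adjusting for period gives 15.0. A split at least this uneven has probability 2 × (1 + 10 + 45 + 120)/1024 = 0.34 under simple randomisation of 10 women.

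The effect of a period term on power at n = 10 is as follows, with the shift in SDs of the difference:
- No period effect: a loss of about 1 point with equal orders and about 6 averaged over simple randomisation.
- Half-SD shift: a gain of about 7 points with equal orders and 3 to 4 averaged.
- One-SD shift: a gain of about 31 points with equal orders and 24 to 25 averaged.

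**The case against.** The strongest reply is that XI.1 states the treatment test first, without covariates, and mentions covariates only for post-hoc work. On that reading the losartan main effect is tested before any covariate enters. The severe power loss also needs four things together that the plan does not state: covariates in the treatment test, treatment-by-covariate terms, uncentred values, and the effect at covariate zero reported as the result. This stands. A reader might infer that following the plan would wipe out the treatment test; the documents do not support that.

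It is also fair to say that adjustment is not always useless in a crossover. Factors that differ between a woman's two visits can matter, and period is one. Time since delivery itself moves by at least 8 weeks between the experimental visits (14 days of washout plus 6 weeks of treatment, VII.E.6), so only its value at entry is a fixed trait. Adjusting for a time-varying nuisance covariate lowered the SD of the estimate from 4.09 to 3.83 in one simulation.

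No section says that blood pressure will be a covariate, or that covariates will be picked after results are seen. The sentence says when post-hoc analyses are done, not when covariates are chosen.

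What the reply does not remove is that post-hoc losartan-placebo comparisons are the same within-woman contrast. The clause has no bias from fixed traits to correct there either, and its role is left open.

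**Conclusion.** The point holds in a limited form. For traits fixed across the two periods, the covariate clause has no confounding to remove. Its likely cost is small: nothing if the terms are additive, and about 1 point of power with one centred interaction term or 9 with four (0.80 to 0.79 and 0.71). The fall to about 7% to 26% is a conditional worst case that the wording leaves possible, not a forecast. On-treatment variables could remove part of the effect under study, and the wording does not rule them out. The omission of period is a separate weakness in the stated model.

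The power figures rest on 10 completers, two-sided testing, a back-solved standardised difference of 0.996, covariates unrelated to the treatment difference, and assumed covariate distributions. The conclusion that fixed traits cannot confound follows from the design and does not depend on them.

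**What to change.** - In XI.1, delete the covariate clause from the losartan-placebo comparisons, both main and post-hoc.
- Add period to the treatment model. If the repeated measures ANOVA is kept, entering randomised order as a between-woman factor does this, because the treatment-by-order term is the period effect.
- State that variables measured on treatment, including blood pressure, will not be adjusted for in these comparisons.
- If effect modification by baseline traits is of interest, name the traits in advance, mean-centre them and report the results as exploratory.

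This changes analysis wording only and needs no extra data or participants. Period takes about one degree of freedom, with a power loss of about 1 to 6 points at n = 10 if there is no period effect. The low end applies if the two orders are equally filled. Any small precision gain from a time-varying nuisance covariate is given up.
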